V.F. Other alarming signs of disease: shortness of breath; cough, etc.

V.G. If bleeding or spotting; refer.

V.H. Breast examination.

VI. Special test

VI.A. Urine: protein for nulliparous or high risk multiparous.

VI.B. Blood: Hb, all.

VII. Assessment and referral

VII.A Reassess risk based on evidence since second visit and observations at present visit:

- untoward symptoms: referral as required
- evidence of preeclampsia; refer to special unit in the clinic, or hospitalize
- suspicion of fetal growth retardation: (symphysis-to-fundus distance too short): refer and arrange for delivery
- suspicion of twins: refer for confirmation, arrange delivery
- urine test positive for protein: refer
- if Hb continuously < 70 g/l: refer and arrange for delivery
- if Hb > 130 g/l: new appointment at 36 weeks, to check fetal growth, blood pressure and proteinuria.

VIII. Intervention

VIII.A. Iron: continue, all. If Hb on first test < 70 g/l, refer.

VIII.B. If bleeding, refer.

VIII.C. Tetanus toxoid, second injection.

IX. Advice, questions & answers, and appointment

IX.A. Repeat advice given at first and second visits.

IX.B. Advice on measures, action in case of (threatened) labour.

IX.C. Questions & answers: time for free communication.

IX.D. Reconfirm written information on where and whom to call in case of emergency or any other need.

IX.E. Recommendations on lactation, contraception and the importance of the postpartum visit.

IX.F. Appointment: fourth visit: at (or close to) 38 weeks.

X. Record keeping

- X.A. Office record.
- X.B. Home based record.

The Fourth Visit

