II.B. Intercurrent diseases, injuries, or other conditions since third visit. Intake of medicines, other than iron, folate.

II.C. Iron intake: compliance.

II.D. Note other medical consultations, hospitalization, sick leave in present pregnancy, since third visit.

III. Obstetric history

Final review of obstetric history relevant to delivery.

IV. Present pregnancy

IV.A. Symptoms, events since third visit: pain contractions (pre-term labour?), bleeding, vaginal discharge (amniotic fluid?). Other specific symptoms or events.

IV.B. Changes in body features or physical capacity, observed by the women herself or by husband, other family members.

V. Physical examination

- V.A. Blood pressure
- V.B. Symphysis-to-fundus distance: record on graph.
- V.C. Multiple fetuses.
- V.D. Fetal lie, presentation (head, breech, transverse).
- V.E. Fetal heart sound(s) by hand-held doppler only if no movements are seen or referred by patient or she asks for it.
- V.F. Generalized edema.
- V.G. Other alarming signs of disease shortness of breath, cough, etc.
- V.H. If bleeding or spotting: refer.

VI. Special tests

Urine: proteinuria, for nulliparous or high risk multiparae.

VII. Assessment and referral

- VII.A. Reassess risk, based on evidence since third visit and observations at present visit.
 - untoward symptoms: referral as required
 - evidence of preeclampsia: refer, or hospitalize
 - suspicion of fetal growth retardation: (symphysis-to-fundus distance too short): refer
 - suspicion of twins: arrange for hospital delivery
 - suspicion of breech presentation: refer. Hospital delivery mandatory.

VIII. Intervention

- VIII.A. Iron: continue, all.
- VIII.B. If bleeding: refer.

IX. Advice, questions & answers, and appointment

- IX.A. Repeat advice given at previous visits.
- IX.B. Advice on measures, action in case of labour, leakage of amniotic fluid.
- IX.C. Advise on breast feeding.
- IX.D. Questions & answers: time for free communication.
- IX.E. Reconfirm written information on whom to call and where to go (place of delivery) in case of labour or any other need.
- IX.F. Appointment: if not delivered by end of week 41 (state date): go to hospital for check-up.
- IX.G. Appointment for post partum visit. Recommendation on lactation and contraception.

X. Record keeping

- X.A. Office record.
- X.B. Home based record.

Women attending late in pregnancy

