It is very likely that a good number of women will not initiate antenatal care early enough in pregnancy to follow the schedule presented above. These women, particularly those starting > 32 weeks of gestation, should have the first visit with cumulative activities of previous visit and after it the ones which correspond to the gestational age. It is expected therefore that the first visit will take more time than a regular first visit. Special care should be taken that all previous activities are conducted at this time.

The Post-Partum Visit

Although the post-partum visit is universally recommended for perinatal care, it is seldom done in most developing countries. The importance of this "post" and "pre-conception care" visit has been recently emphasized by the expert panel on prenatal care (Rosen et al., 1991). The determinants of some pregnancy outcomes, such as low birth weight and the

Table 3 : CONTENT OF THE BASIC COMPONENT OF THE
NEW ANTENATAL CARE PROGRAMME

ACTIVITY	PRENATAL VISITS (approximate week gestation)			
	1st *	2nd (26 wk)	3rd (32 wk)	4th (38 wk)
Pregnancy test (only if req. at 1st trimester & no clinical evidence of preg.)	☒	--	--	--
Medical/Ob history (risk evaluation)	■	--	--	--
Question of Rh immunization with fetal/newborn disease in previous pregnancy	☒ multiparous	--	--	--
Complete clinical examination	■	--	--	--
Clinical examination for severe anemia	■	■	■	■
Ob exam (+) Gyn exam/detection of symptomatic STDs	■ routine vaginal exam **	■ ob exam	■ ob exam	■ ob exam
Maternal weight/height	■	--	--	--
Maternal weight (follow-up)	--	☒	☒	☒
Uterine height	■	■	■	■
Gestational age assessment	■	■	■	■
Blood pressure	■	■	■	■
- Blood type / Rh	■	--	--	--
- Hb	☒	☒	■	--
- Syphilis	■	--	--	--
- Urine test	■ ***	☒	☒	☒
Tetanus toxoid	■	--	■	--
Folic acid/Iron supp.	■	■	■	■
Fetal heart rate	☒	☒	☒	☒

■ for all women
 * for all women at first contact with clinic, regardless of gestational age
 ** could be postponed to second or third visit
 ☒ only in some cases:
 a) proteinuria: nulliparous or with previous preeclampsia or hypertension;
 b) fetal heart rate: only if requested or no fetal movements seen or reported;
 c) maternal weight: only those with low weight/height at 1 visit or obese women
 d) anemia: ☒ only if signs of severe anemia
 *** multiple dipstick
 (+) ob exam: # fetuses, fetal situation & presentation

Table 3 : CONTENT OF THE BASIC COMPONENT OF THE
NEW ANTENATAL CARE PROGRAMME
(cont'd)

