ACTIVITY	PRENATAL VISITS (approximate week gestation)			
	1st *	2nd (26wk)	3rd (32 wk)	4th (38 wk)
Recommendations for: urgent consultation next visit/schedule treatment/medical conditions	■	■	■	■ date of wk 41 and instructions
Referral to hospital if needed	⊗	⊗	⊗	⊗
Detection of breech presentation & referral for external version	—	—	—	■
Instruction for referral for adequate level of delivery	—	—	⊗	⊗
Recommendations for lactation			■	■
Contraception	—	—	■	■
Pre-conceptual care	—	—	—	⊗
Activities to reduce smoking	■	■	■	■

■ for all women * for all women at first contact with clinic, regardless of gestational age ⊗ only in some cases: delivery: if previous obstructed labor, hemorrhage or C.S.; pre-conceptual care: infant with NTD or other congenital malformation
				

Table 4 : BASIC ANTENATAL CARE PLAN BY VISIT

The First Visit

- Medical/Ob history (risk evaluation)
- Clinical examination / severe anemia
- Ob exam / Gyn exam (can be postponed until second visit)
- Maternal weight / height
- Blood pressure
- Gestational age estimation
- Uterine height
- Syphilis, detection of symptomatic STDs
- Urine test (multiple dipstick)
- Tetanus toxoid
- Fe / Folic acid supplementation
- Recommendation for urgencies / hot line for emergencies
- Complete antenatal card
- Blood type and Rh

The Second Visit and subsequent visits

- Blood pressure to nulliparous & women with previous preeclampsia/age groups
- Obstetric exam
- Gestational age estimation
- Fetal heart rate
- Uterine height
- Urine test (only nulliparous/women with previous preeclampsia)
- Fe / Folic acid supplementation
- Clinical examination for anemia
- Maternal weight (only women with low weight/height 1st visit)
- Recommendation for urgencies
- Complete antenatal card

For the Third Visit - add:

- Repeat syphilis & g.c. test for high-risk women
- Hb
- Tetanus toxoid (second dose)
- Instructions for adequate place of delivery
- Recommendations for lactation / contraception

For the Fourth Visit - add:

- Detection of breech presentation & referral for external version

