4.5 The Control Group

Traditional antenatal care presupposes monthly visits from the start (as early as possible) to week 28, then visits at two-weekly intervals until week 36, followed by weekly intervals until birth or the end of week 42, at which time post-term referral is common for those who have not yet developed spontaneous labour contractions.

Although this timing is not implemented exactly in all study settings, it is close to most of the recommendations and the actual care provided in private practices in the developing world. There would not be major disagreements among obstetricians in identifying this as the "ideal" programme. The contents of each visit may vary according to the location, for example, regarding screening test. In principle, however, the same routine elements are included in each visit. In practical terms, few public clinics in urban areas of developing countries complete this protocol, even for those women who attend early in pregnancy.

During the preparatory stage of the study, a survey was conducted in all clinics for a baseline description of antenatal care procedures and available resources, adapted from a study recently conducted in Europe (Maratos, 1986). This survey included a random sample of antenatal care visits taken at baseline and once more during the study. A simplified form was filled out, including information on crucial elements of content, interventions and use or resources in both the control and intervention clinics. Clinics, randomized to continue with the traditional care, serve as the comparison group. The personnel were informed of the study and its objectives, before randomization and it is expected that the clinics will themselves update their procedures and attempt to follow the recommended (Western type) protocols more closely (Hawthorne effect). As the main factors related to the present organization of prenatal care have not been changed, this improvement may not be totally achieved; however, it is very likely that the control clinics will offer, particularly to those women attending in early pregnancy, a prenatal care programme more efficient than the one in place before the study was initiated.

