4.8 Sample Size

4.8.1 Background

Sample size estimates depend on a number of practical and statistical considerations, some of which can only be surmised and several of which are somewhat arbitrary. Factors that influence sample size are:

1. major outcome variables of interest;
2. pre-intervention level of the major end-points, and the variability of the endpoints in the absence of intervention;
3. effect of intervention on the endpoints selected for study;
4. the chance of claiming that an effect intervention has occurred, when in fact, no effect was present: the alpha level corresponding to the statistical test of significance;
5. the chance of failing to detect an effect of intervention, when in fact, an effect was present: $\beta = 1 - \text{power of the test of significance}$;
6. participation rates of both individuals and entire clusters;

Table 6 : Outcomes of the ANC Randomized Controlled Trial

A. PRIMARY OUTCOMES	Question number in Data Collection Form(s)	Rate
Rate of maternal morbidity indicator index ⁽⁺⁾	See individual items	> 10%
Rate of LBW (<2500g)	50	> 10%
B. SECONDARY OUTCOMES		
Incidence of proteinuric ^(*) -pre-eclampsia or eclampsia	27	
Prevalence of post partum anemia (hemoglobin <90g/l) ^(**)	38	
Incidence of severe urinary tract infection/pyelonephritis (requiring antibiotic treatment ^(***) or hospitalization)	28 and hospital admission	
Rate of treated syphilis and any other STDs	31	
Rate of post-partum positive syphilis test ^(***) (among women without treatment during pregnancy)	39	
Rate of incomplete tetanus immunization	21	
Rate of post partum hospital stay ≥ 7 days for maternal complications	41-42	
Rate of IUGR ^(#)		
Rate of preterm delivery (<37 weeks)	52	
Rate of spontaneous & PROM pre-term delivery : <35weeks : 35-36 weeks	36	
Rate of medically indicated pre-term delivery : <35 weeks : 35-36 weeks	36-37	
Rate of breech presentation at birth	48	
Rate of very LBW (<1500 g)	50	
Rate of Apgar score <5 at 5'	53	
Rate of I.C.U. stay > 2 days	55 (c)	
Rate of fetal death	49	
Rate of pre-discharge neonatal death	56	

* Proteinuria of 2.0 g or more in 24h or 2+ or more on qualitative examination (dipstick)

** Requires postpartum blood samples

*** Excluding the antibiotics given to treat asymptomatic bacteriuria

+ Maternal morbidity indicator index: the presence of at least one of the following:

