16. Any previous surgery on reproductive tract? (Myomectomy, removal of septum, cone biopsy, classical CS, cervical cerclage)	
1 = No 2 = Yes	
17. Iso-immunization Rh(-) in current or in previous pregnancy	
1 = No 2 = Yes	

ANTENATAL CARE	
18. First day of the last normal menstrual period	day month year 
19. Date of first antenatal visit	day month year 
20. Visits to antenatal care or hospital outpatient clinics	Gestational age
a) 1st visit	Completed weeks 
b) 2nd visit	
c) 3rd visit	
d) 4th visit	
e) 5th visit	
21. Total number of visits:	
a) to the original antenatal care clinic	
b) to any other antenatal clinic	
c) to a hospital high risk clinic	

163

Subject number

Grid for subject number

22. Tetanus immunization

- 1 = No
2 = Incomplete (1 dose)
3 = Yes (complete 2 doses)
4 = Previously immunized (1 dose)

23. a) Iron supplementation

- 1 = No 2 = Yes
3 = Contraindicated

b) If Yes, gestational age when supplementation started Weeks

24. a) Referred to higher level of antenatal care

- 1 = No 2 = Yes

If No, go to Q 26

1st 2nd

b) If Yes, gestational age at referral

Grid for gestational age at referral

25. Principal reason for referral

- 1 = No 2 = Yes

- a) Pregnancy induced hypertension
b) Pre-eclampsia
c) Severe anaemia (< 70 g/l)
d) Chronic hypertension
e) Uterine height low for gestational age
f) Malpresentation or breech
g) Multiple gestation
h) Pyelonephritis or urinary infection
i) Vaginal bleeding
j) Diabetes mellitus
k) Cardiac disease
l) Chronic respiratory conditions
m) Renal disease
n) Pelvic mass
o) Isoimmunization Rh(-)
p) Other

Grid for principal reason for referral (1st and 2nd)

26. After referral, the mother

- 1 = Continued care at higher level of antenatal care
2 = Was referred back to the original antenatal care clinic (or level)
3 = Was scheduled for hospital admission (complete Form 2 - AHA)

Grid for referral outcome (1st and 2nd)

27. Any hospital admission during the antenatal period

- 1 = No 2 = Yes

MATERNAL EVENTS DURING PREGNANCY

28. Hypertensive disorders of pregnancy

- 1 = No 2 = Yes

- a) Only hypertension, no treatment
b) Only hypertension with treatment or referral
c) Pre-eclampsia (hypertension and proteinuria)

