d) Pre-eclampsia admitted to hospital
e) Eclampsia

29. Urinary tract infection

- 1 = No
2 = Yes, no treatment
3 = Yes, with antibiotic treatment
4 = Yes, with hospital admission

30. Vaginal bleeding during pregnancy

- 1 = No 2 = Yes

- a) First trimester
b) Second trimester
c) Third trimester

31. Lowest haemoglobin value during pregnancy g/l

Grid for lowest haemoglobin value

32. Was the mother treated for any of the following conditions during pregnancy?

- 1 = No 2 = Yes

- a) Trichomoniasis, moniliasis or any other abnormal discharge
b) Syphilis
c) Any other sexually transmitted diseases

33. Was external version for breech or malpresentation attempted?

- 1 = No, cephalic presentation
2 = Breech or malpresentation, no version attempted
3 = Version attempted

34. Prelabour rupture of membranes

- 1 = No 2 = Yes

164

Subject number

Grid for subject number

LABOUR AND DELIVERY

35. At admission in labour, did the mother have any of the following conditions?
1 = No
2 = Yes, noted during antenatal period
3 = Yes, first noted at admission

- a) Pregnancy induced hypertension
b) Pre-eclampsia
c) Severe anaemia (< 70 g/l)
d) Chronic hypertension
e) Uterine height low for gestational age
f) Malpresentation or breech
g) Multiple gestation
h) Pyelonephritis or urinary infection
i) Vaginal bleeding
j) Diabetes mellitus
k) Cardiac disease
l) Chronic respiratory conditions
m) Renal disease
n) Pelvic mass
o) Isoimmunization Rh(-)
p) Other

36. Fetal heart rate present at admission in labour
1 = No 2 = Yes

37. Onset of labour
1 = Spontaneous
2 = Induction (Complete Question 38)
3 = Elective caesarean section

38. Indications for induction of labour
1 = No 2 = Yes

- a) Prelabour rupture of membranes
b) Post-term
c) Intrauterine growth retardation
d) Chronic fetal distress
e) Pre-eclampsia
f) Maternal medical complications
g) Pregnancy complications
h) Isoimmunization Rh(-)

POSTPARTUM INFORMATION

39. Lowest haemoglobin value g/l

Grid for haemoglobin value

40. Syphilis test
1 = Negative 2 = Positive

Grid for syphilis test

41. a) Maternal death
1 = No 2 = Yes
b) If Yes, cause of death

Grid for maternal death

ICD-10 code

42. Date of mother's discharge from hospital or death

Grid for date of discharge

NEONATAL OUTCOME

43. Date of delivery or abortion

Grid for date of delivery

44. Time of delivery

Grid for time of delivery

45. Total number of fetuses

Grid for total number of fetuses

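### Urine-protein testing follows the allocated programme, so ascertainment of proteinuric pre-eclampsia depends on the arm; the primary index moves little, the secondary outcome possibly more

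*Protocol*

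**What the plan says.** **New programme.** Protocol section 4.4.2, Table 3, gives every woman a multiple dipstick at visit 1. At visits 2 to 4 the urine test is marked for some women only, with the footnote "a) proteinuria: nulliparous or with previous preeclampsia or hypertension". Other places word the selection differently:

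- Table 4, second and later visits: "Urine test (only nulliparous/women with previous preeclampsia".
- Third visit, list of special tests: "Urine: protein for nulliparous or high risk multiparous".
- Fourth visit: "Urine: proteinuria, for nulliparous or high risk multiparae".
- The Appendix I checklist narrows the history criterion to previous eclampsia.
- Table 2 describes a protein dipstick at the first and later visits with no restriction.

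**Control care.** Section 4.5 says that "the same routine elements are included in each visit". It offers this as a principle, and says just before it that screening tests may vary by location. The usual-care description for Khon Kaen (section 4.3) names haematocrit and syphilis serology, not urine protein.

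**Outcome.** Section 4.7.2 puts proteinuric pre-eclampsia in the primary maternal morbidity index. Table 6 lists proteinuric pre-eclampsia or eclampsia as a secondary outcome, with the threshold "Proteinuria of 2.0 g or more in 24h or 2+ or more on qualitative examination (dipstick". The Appendix I Summary form records it at item 28c as "Pre-eclampsia (hypertension and proteinuria". Item 35 asks "At admission in labour, did the mother have any of the following conditions" and separates conditions noted antenatally from those first noted at admission.

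**The concern.** A case can be recorded only if someone tests the urine. In the new arm, a parous woman without the listed history has no routine protein test after visit 1, and there are fewer visits at which to find disease. Whether she is counted therefore depends partly on the programme to which her clinic was allocated.

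Section 4.2.3 discusses staff knowledge of allocation and improvement in the control clinics, but not unequal testing. Nothing in the protocol requires the same urine test in both arms, for example at admission for delivery.

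This matters because section 4.8.1 treats the index as something the new programme must show does not rise. Under-recording in that arm would push towards such a conclusion. It could also make the secondary outcome look like a benefit.

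**Working it through.** All counts are from Khon Kaen, both arms pooled; the protocol gives none by arm or for the other sites.

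**Inputs**
- Table 24, of 6354 women: pre-eclampsia 9, pre-eclampsia admitted to hospital 12, eclampsia 4. Total 9 + 12 + 4 = 25.
- Section 5.2.7: index incidence 8.3%.
- Section 5.2.6: severe postpartum anaemia 403. Section 5.2.4: urinary infection treated with antibiotics or admitted, 84 + 29 = 113.
- Section 5.2.3: median visits 4 (new) and 7 (control).
- Table 21, row labelled primipara (read as no previous birth): 3062. Over the 6560 women of the neighbouring tables, the parous share is 1 − 3062/6560 = 53.3%.

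**Check of the index figure.** 403 + 113 + 25 = 541, and 541/6354 = 8.5%. The stated 8.3% is 0.083 × 6354 ≈ 527 women. The gap of 14 is compatible with women who have more than one component.

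**Share of the index.** 25/527 = 4.7%. This is an upper limit, because a woman with a second component stays in the index even if her pre-eclampsia is missed.

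**Formula, with no true effect and full recording in control**
- Apparent relative risk = 1 − e × s × u
- Relative shift of the index = 4.7% × e × s × u

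Here e is the share of cases exposed to under-recording, s the share of those in women not routinely tested after visit 1, and u the share of those that go unrecorded. The protocol gives none of the three. Assume s = 0.5 and u = 0.3 to 0.6.

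| Case | e | e × s × u | Apparent relative risk | Index shift |
|---|---|---|---|---|
| All 25 exposed | 1 | 0.15 to 0.30 | 0.85 to 0.70 | 0.7% to 1.4% |
| Only the 9 non-admitted exposed | 9/25 = 0.36 | 0.054 to 0.108 | 0.95 to 0.89 | 0.25% to 0.5% |

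The second row assumes that the 4 eclampsia and 12 admitted cases come to light clinically in either arm.

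**Cross-check with other assumptions.** Take the 21 pre-eclampsia cases (21/6354 = 0.33%), equal risk by parity, and 25% to 50% of parous cases unrecorded. The relative risk for pre-eclampsia is 1 − 0.533 × (0.25 to 0.50) = 0.87 to 0.73, and the index odds ratio is 0.994 to 0.988.

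**Yardstick.** The trial is sized for an odds ratio of 1.18, that is 0.10 against 0.116, a relative change of 16%. The largest index shift above is 1.4%.

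**The case against.** The strongest objection concerns direction. Control-arm protein testing is not given, the statement in section 4.5 is one of principle, and the same section says few public clinics complete the traditional schedule. A control site with little routine dipstick use could test less than the new arm, which tests every woman once and nulliparous women repeatedly. This stands. A reader might infer that the bias certainly favours the new programme; the documents make that likely, not established.

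Second, detection has other routes. Table 3 measures blood pressure in all women at every visit, raised pressure leads to referral, and the index window runs to 24 hours after delivery. This partly stands and is why the narrow row is shown. Table 4, however, words blood pressure at later visits as selective too.

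Third, dummy Table IV compares the number of urine tests by arm, the content survey forms record dipstick use, and an unseen analysis plan could add a sensitivity analysis. But Table IV describes the two policies and is not tied to the outcome. The pairing of arm-specific testing with a protein-defined outcome is fixed in this protocol.

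A reader might also want to replace the secondary outcome with pre-eclampsia at labour admission. The documents do not support that. Code 2 of item 35 still reflects antenatal detection, onset after admission is missed, and section 4.3 says about 90% of women deliver where they had antenatal care, so delivery hospitals in Khon Kaen are largely separate by arm.

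**Conclusion.** The concern holds as one of arm-dependent ascertainment, with a likely but unproven direction that may differ by site. At Khon Kaen rates the primary index is little affected, by about 0.25% to 1.4% in relative terms. For the secondary outcome, the apparent relative risk with no true effect is about 0.70 to 0.95: 0.70 to 0.85 if all 25 cases are exposed to under-recording, 0.89 to 0.95 if only the 9 non-admitted ones are. These ranges rest on the assumed s and u. Taking half of the cases to be in untested women is probably high, since high-risk parous women are tested.

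A reader might infer that the primary comparison is seriously compromised. That would need much more pre-eclampsia than is documented. With an assumed 1% to 3% of women affected, an index of 10% and 25% to 50% of parous cases unrecorded, the index odds ratio under no true effect would be 0.985 to 0.912. The protocol gives no pre-eclampsia rate for the other three sites, and Khon Kaen, which recruited 6765 of about 20,000 women, recorded 0.33%.

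**What to change.** Keep the outcomes as defined, and before the pooled comparison is run:

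1. Pre-specify a sensitivity analysis of the secondary outcome and of the index, with the pre-eclampsia/eclampsia part limited to forms less dependent on routine antenatal dipsticks: eclampsia (item 28e), pre-eclampsia admitted to hospital (item 28d) and pre-eclampsia present at labour admission (item 35b).
2. Tabulate item 35b by arm, first noted at admission against noted antenatally, and read it with the number of urine tests in dummy Table IV. Fewer tests and more first-noted-at-admission cases in one arm would point to antenatal under-detection there.
3. Add unequal urine testing to the limitations in section 4.2.3, with the direction stated as likely but not established.
4. Reconcile Tables 2, 3 and 4, the visit texts and the checklist on who is tested. Which rule is right is not a statistical question.

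Item numbers are those of the Appendix I form; Table 6 cites question 27 for pre-eclampsia.

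The cost is one derived variable and one table from items already collected. The limit is that admission testing is not standardised and hospital admission can itself follow a clinic dipstick, so the bias is reduced and made visible, not removed.

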The third visit should take place around the 32nd week and is expected to take 20 minutes. The examinations and tests are restricted to measuring blood pressure, symphysis-to-fundus measurement, a urine test for primiparous and those with history of hypertension

preeclampsia and eclampsia, and hemoglobin on all. Special attention should be directed toward discovery of twins during the external abdominal examination and uterine height measurement.

Referrals are based on symptoms and findings which require special intervention. For example, high haemoglobin (> 130 g/l) in absence of other symptoms may mean poor fetal nutrition, warranting an extra visit at week 36 to evaluate fetal growth.

As some of the women will go into labour and deliver before the next scheduled visit, extra attention must be given to instructions and advice in the event labour starts (pains or leaking of amniotic fluid). Written instructions should reconfirm the advice, and plans for getting to hospital should be reviewed. The importance of a post-partum visit, including recommendations for lactation and conception, is stated to ensure that the women is seen at the clinic within the two months post-partum.

Content of the third visit:

I. Personal information

Note any changes or events since second visit.

II. Medical history

- II.A. Review relevant issues of medical history as recorded at first and second visits.
- II.B. Intercurrent diseases, injuries, or other conditions since second visit. Intake of medicines, other than iron, folate.
- II.C. Iron intake: compliance.
- II.D. Note other medical consultations, hospitalization, sick leave in present pregnancy.

III. Obstetric history

Review relevant issues of obstetric history as recorded at first visit, and as checked at second.

IV. Present pregnancy

IV.A. Symptoms, events since second visit: pain (pre term labour?), bleeding, vaginal discharge (amniotic fluid?). Other specific symptoms or events.

IV.B. Changes in body features or physical capacity, observed by the women herself, husband, or other family members.

IV.C. Fetal movements.

IV.D. Check-up on habits: smoking, alcohol, other.

V. Physical examination

V.A. Blood pressure

V.B. Symphysis-to-fundus distance: record on graph.

V.C. Palpate for multiple fetuses.

V.D. Fetal heart sounds; use hand-held doppler only if no fetal movements are seen, mother feels less fetal movement or she requests it.

V.E. Generalized edema.

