Patient's Name _____ Clinic Record No. _____ Study Subject No. ____/____/____/____

FIRST VISIT for all women at first contact with clinics, regardless of gestational age. If first visit later than recommended, carry out all activities up to that time DATE: / /	Visits			
	1st <12 wks	2nd	3rd	4th
Classifying Form indicates eligibility for the basic programme				
Clinical examination				
Clinically severe anemia: Hb test				
Ob exam : gestational age estimation, uterine height				
Gyn exam (can be postponed until second visit)				
Blood pressure				
Maternal weight / height				
Rapid syphilis test, detection of symptomatic STDs - treatment				
Urine test (multiple dipstick)				
Blood type and Rh				
Tetanus toxoid				
Fe / Folic acid supplementation				
Recommendation for emergencies / hot line for emergencies				
Complete antenatal card				
SECOND VISIT and SUBSEQUENT VISITS DATE: / /	Gestational age - approx. # of weeks: 26 32 38			
Clinical examination for anemia				
Ob exam: gestational age estimation, uterine height, fetal heart rate				
Blood pressure				
Maternal weight (only women with low weight at first visit)				
Urine test for protein (only nulliparous/women with previous eclampsia)				
Fe / Folic acid supplementation				
Recommendation for emergencies				
Complete antenatal card				
THIRD VISIT: add DATE: / /				
Hemoglobin				
Tetanus toxoid (second dose)				
Instructions for delivery				
Recommendations for lactation / contraception				
FOURTH VISIT: add DATE: / /				
Detection of breech presentation & referral for external version				
Complete ANC card, recommend it be brought to hospital				

Staff responsible for antenatal care: Name _____

Batch Cover Form

To be Completed by the Investigator

Clinic Name

Clinic/Hospital number

Name and Signature of Investigator

Date batch sent

Summary of Batch Contents

Form name	No of forms
CLA	
SUM	
AHA	
MUL	

To be Completed By Coordinating Centre

Batch Number Allocated

Date batch received

Date batch processed

Date Query sheet produced

Remarks

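### Table 4 restricts blood pressure after the first visit to a subgroup, while Table 3, the third- and fourth-visit lists and the checklist do not

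*Protocol*

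**What the plan says.** Table 4 in protocol section 4.4.2 sets out the basic care plan by visit. At the first visit it lists blood pressure with no qualifier. Under the heading for the second and subsequent visits it reads "Blood pressure to nulliparous & women with previous preeclampsia/age groups". The lists of items to add at the third and fourth visits do not restore the measurement for other women. Table 4 also has a separate urine line with its own, similar restriction.

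The other readable sources differ:

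- Table 3 has a row "Blood pressure" carrying the all-women symbol at each of the four visits. Its key to items for some women only does not name blood pressure. The matching restriction there is "a) proteinuria: nulliparous or with previous preeclampsia or hypertension".
- The third-visit text says "The examinations and tests are restricted to measuring blood pressure, symphysis-to-fundus measurement, a urine test for primiparous", which limits the urine test and not the blood pressure. The third-visit content list has blood pressure unqualified, and separately "VI.A. Urine: protein for nulliparous or high risk multiparous".
- The fourth-visit content list has "V.A. Blood pressure" unqualified and restricts only the urine test. Its referral section includes "evidence of preeclampsia: refer, or hospitalize".
- The basic antenatal care checklist in Appendix I lists blood pressure unqualified for the second and subsequent visits, next to "Urine test for protein (only nulliparous/women with previous eclampsia".

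**The concern.** The protocol gives two rules for one element of the intervention. Blood pressure is the main routine means of finding hypertensive disease between the first visit and labour. Table 2 lists its measurement as an intervention in its own right, with the percentage of women measured as a process indicator.

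Under the Table 4 rule, a parous woman on the basic component, without previous pre-eclampsia and outside the unspecified age groups, would have neither blood pressure nor urine protein checked at any scheduled visit after the first. That is a safety gap confined to the new arm.

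It is also a problem of definition. Section 4.7.4 says the intervention will be described and compliance with it documented, and compliance cannot be judged against two rules. The Executive Summary and section 4.11 foresee recommendations and a detailed publication if the model succeeds, and a compact by-visit table is easily copied into such material.

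**Working it through.** **Side-by-side reading.** The protocol states no figure for this point, so the check is a comparison of every readable place that fixes blood pressure after the first visit.

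| Source | Blood pressure | Urine protein |
|---|---|---|
| Table 4, second and later visits | Subgroup only | Subgroup only (own line) |
| Table 3, visits 2 to 4 | All women | Subgroup only |
| Third-visit text and list | No restriction | Subgroup only |
| Fourth-visit list | No restriction | Subgroup only |
| Appendix I checklist | No restriction | Subgroup only |

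Three things follow.

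1. Table 4 is the only outlier. The other sources mark a restriction where they mean one, and they put it on urine protein.
2. This does not look like an artefact of text extraction. Table 4 has both a restricted blood pressure line and a separate restricted urine line, so the first is not simply the second misplaced.
3. The second-visit content list is incomplete in the text at hand. For visit 2 the comparison therefore rests on Table 3 and the checklist.

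**Who would be affected if a clinic followed Table 4.** Inputs are from Khon Kaen only:

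- Parous: 1 − 3062/6560 = 0.533 (Table 21, reading its primipara row as no previous birth; the baseline survey in Table 11 also gives 53.3% parous).
- Eligible for the basic component: 3053/3379 = 0.904 (Executive Summary).
- Aged 20 to 34: 5032/6560 = 0.767 (Table 19).

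Shares of new-arm women:

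- Parity and eligibility independent, no age exemption: 0.533 × 0.904 = 0.482.
- As above, with the age groups taken to mean under 20 and 35 or over, and age independent of the rest: 0.482 × 0.767 = 0.370.
- Every ineligible woman parous, no age exemption: 0.533 − (1 − 0.904) = 0.437.
- As above, with the same age exemption: 0.437 × 0.767 = 0.335.

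The range is about 34% to 48%. It depends on guesses about the age groups and would be lower if they were broader. Parous women with previous pre-eclampsia are not subtracted; Table 11 puts such a history at 0.3% of women.

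**What can be said about the index.** The rows of Table 24 add to its total: 32 + 2 + 9 + 12 + 4 + 6295 = 6354. Pre-eclampsia and eclampsia together are (9 + 12 + 4)/6354 = 0.39%, both arms pooled. The hypertension rows carry no severity category, so severe hypertension, also a component of the index (section 4.7.2), cannot be counted.

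**The case against.** The strongest reply is that this is a drafting slip in a summary list. Every other readable source leaves blood pressure unrestricted. Clinics had a detailed clinical manual (section 4.4.2) that is not shown. At Khon Kaen the unrestricted checklist was built into the medical record, and before randomization 96.7% of surveyed women there had blood pressure measured (Table 12). The fourth-visit referral rule sits in a list that itself orders blood pressure, so a clinic working from that list would measure it. Age cut-offs might stand in the Classifying form or the manual. Delivery is already to be checked through monthly visits with case review (section 4.9.2) and dummy Table IV, which counts blood pressure measures by arm.

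All of that stands, and it is why the point is minor. It does not remove the contradiction: Table 4 is a by-visit care instruction in the current text, and nothing in the protocol says which source takes precedence.

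A reader might infer that new-arm women actually went without blood pressure checks. The documents do not support this; no site is shown to have used the Table 4 rule, and the 34% to 48% comes from the one site shown to have used the unrestricted checklist.

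A reader might also multiply 0.39% by those shares, get 0.13 to 0.19 percentage points, and take that as a ceiling on the loss to the index. It is not one. It assumes cases spread evenly by parity, and it leaves out severe hypertension, the component that blood pressure detects most directly.

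**Conclusion.** The contradiction is real and Table 4 is wrong as written, most likely because a restriction meant for urine protein was attached to blood pressure. It is a minor error of safety and intervention definition. The only size that can be given is conditional: roughly a third to a half of new-arm women if a clinic followed Table 4, on Khon Kaen figures and the stated assumptions about parity, eligibility and age.

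The effect on the maternal morbidity index is neither shown to exist nor bounded. Even under the literal rule, detection would be reduced or delayed and not abolished. First-visit blood pressure, unscheduled visits, conditions recorded at admission in labour (Summary form, question 35) and the index window to 24 hours after delivery would remain. A claim that the primary comparison is biased would go beyond the documents.

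**What to change.** 1. Change the Table 4 line for the second and subsequent visits to: Blood pressure (all women).
2. Make sure the corrected line is the one carried into any published or recommended version of the programme.
3. Notify any intervention clinic still active. There are probably none: section 4.14 ends recruitment in October 1997 and follow-up by April 1998, and Khon Kaen finished follow-up on 31 October 1997.
4. To confirm which rule was delivered, split the blood pressure data already planned by previous births within the intervention clinics. The content survey in the last 3 months of recruitment covers women after their first visit (section 4.9.2). Its patient form records blood pressure at the last visit (item 30), and items 10 and 11 give live births and stillbirths or neonatal losses. Where the data behind dummy Table IV allow, apply the same split to the number of blood pressure measures.

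The cost is one corrected line and one extra tabulation of data the protocol already collects. Sample size, endpoints and the main analysis do not change.
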